6.4 Contraception/Pregnancy/Nursing

6.4.1 Contraception

MK-3475 may have adverse effects on a fetus in utero. Furthermore, it is not known if MK-3475 has transient adverse effects on the composition of sperm. Non-pregnant, non-breast-feeding women may be enrolled if they are willing to use 2 methods of birth control or are considered highly unlikely to conceive. Highly unlikely to conceive is defined as 1) surgically sterilized, or 2) postmenopausal (a woman who is \geq 45 years of age and has not had menses for greater than 1 year will be considered postmenopausal), or 3) not heterosexually active for the duration of the study. The two birth control methods can be either two barrier methods or a barrier method plus a hormonal method to prevent pregnancy. Subjects should start using birth control from study Visit 1 throughout the study period up to 120 days after the last dose of study therapy.

The following are considered adequate barrier methods of contraception: diaphragm, condom (by the partner), copper intrauterine device, sponge, or spermicide. Appropriate hormonal contraceptives will include any registered and marketed contraceptive agent that contains an estrogen and/or a progestational agent (including oral, subcutaneous, intrauterine, or intramuscular agents).

Subjects should be informed that taking the study medication may involve unknown risks to the fetus (unborn baby) if pregnancy were to occur during the study. In order to participate in the study they must adhere to the contraception requirement (described above) for the duration of the study and during the follow-up period defined in section 7.2.2-Reporting of Pregnancy and Lactation to the Sponsor and to Merck. If there is any question that a subject will not reliably comply with the requirements for contraception, that subject should not be entered into the study.

6.4.2 Use in Pregnancy

If a subject inadvertently becomes pregnant while on treatment with MK-3475, the subject will immediately be removed from the study. The site will contact the subject at least monthly and document the subject's status until the pregnancy has been completed or terminated. The outcome of the pregnancy will be reported to the Principal Investigator and to Merck without delay and within 24 hours if the outcome is a serious adverse experience (e.g., death, abortion, congenital anomaly, or other disabling or life-threatening complication to the mother or newborn). The study investigator will make every effort to obtain permission to follow the outcome of the pregnancy and report the condition of the fetus or newborn to the Sponsor. If a male subject impregnates his female partner the study personnel at the site must be informed immediately and the pregnancy reported to the Sponsor and to Merck and followed as described above and in Section 7.2.2.

6.4.3 Use in Nursing Women

It is unknown whether MK-3475 is excreted in human milk. Since many drugs are excreted in human milk, and because of the potential for serious adverse reactions in the nursing infant, subjects who are breast-feeding are not eligible for enrollment.

6.5 Subject Discontinuation Criteria

Subjects may withdraw consent at any time for any reason or be dropped from the trial at the discretion of the investigator should any untoward effect occur. In addition, a subject may be withdrawn by the investigator or the Principal Investigator if enrollment into the trial is inappropriate, the trial plan is violated, or for administrative and/or other safety reasons. Specific details regarding discontinuation or withdrawal are provided in Section 8.1.5.

A subject must be discontinued from the trial for any of the following reasons:

- The subject or legal representative (such as a parent or legal guardian) withdraws consent or decides to discontinue study therapy for any reason.

- Confirmed radiographic disease progression according to modified response criteria (see section 10.2).
- Unacceptable adverse experiences
- Intercurrent illness that prevents further administration of treatment
- Investigator's decision to withdraw the subject
- The subject has a confirmed positive serum pregnancy test
- Noncompliance with trial treatment or procedure requirements
- The subject is lost to follow-up
- Completed 24 months of treatment with MK-3475

Note: 24 months of study medication is calculated from the date of first dose. Subjects who stop MK-3475 after 24 months may be eligible for up to one year of additional study treatment if they progress after stopping study treatment provided they meet the requirements detailed in Section 8.1.6.1.2

- Administrative reasons

The End of Treatment and Follow-up visit procedures are listed in Section 7 (Protocol Flow Chart) and Section 8.1.6 (Visit Requirements). After the end of treatment, each subject will be followed for 30 days for adverse event monitoring. Subjects who discontinue for reasons other than progressive disease will have post-treatment follow-up for disease status until disease progression, initiating a non-study cancer treatment, withdrawing consent or becoming lost to follow-up. After documented disease progression each subject will be followed by telephone for overall survival until death, withdrawal of consent, or the end of the study, whichever occurs first.

6.6 Subject Replacement Strategy

Patients will only be replaced if the patient withdraws consent before the first dose of therapy.

7.0 TRIAL FLOW CHART

7.1 Study Flow Chart

Trial Period:	Treatment Cycles									Safety Follow-Up/ EOT	Progression Free Follow-Up Phase ¹¹	Survival Follow-Up	
	Treatment Cycle/Title:	Main Study Screening (Visit 2)	1	2	3	4	To be repeated beyond 8 cycles						
							5	6	7				8
Scheduling Window (Days):	-28 to -1		±3	±3	±3	±3	±3	±3	±3	~30 days after last dose/ before initiation of new tx	Every 12 weeks +/- 2weeks	Every 12 weeks +/- 2 weeks	
Informed Consent	X												
Inclusion/Exclusion Criteria	X												
Medical History/Physical ¹	X	X	X	X	X	X	X						
Medication Review ²	X	X	X	X	X	X	X	X	X	X			
Trial Treatment Administration ³		X	X	X	X	X	X	X	X				
Survival Status												X	
Review Adverse Events		X	X	X	X	X	X	X	X	X			
Full Physical Examination ¹	X												
Directed Physical Examination ¹		X	X	X	X	X	X		X	X			
Vital Signs and Weight ³	X	X	X	X	X	X	X	X	X	X			
ECOG Performance Status ³	X	X	X	X	X	X	X		X	X			
Pregnancy Test – Urine or Serum β-HCG ⁴	X												
CBC with Differential ⁵	X	X	X	X	X	X	X	X	X	X			
Comprehensive Serum Chemistry Panel ⁵	X	X	X	X	X	X	X	X	X	X			
Urinalysis	X												
T3, FT4 and TSH ⁶	X				X				X				
Tumor Imaging ⁷	X		X		X		X				X		
Archival Tissue Collection ⁸	X												
Correlative Studies Blood Collection ⁹		X	X	X									
Retreatment ¹⁰													

1. Patients should undergo a detailed history and physical examination during screening. A full examination, to be performed to determine eligibility, means that based on the patient's medical history and all relevant systems have been examined. All patients should undergo a focused history and physical examination during each treatment day for the first 6 cycles. After the first 6 cycles history and physical examination can be performed every other cycle.
2. All medications need to be reviewed at screening visit. During follow up visits any changes in medications should be documented.
3. MK-3475 will be administered at a dose of 200 mg IV every 3 weeks for a maximum of 2 years. Prior to each administration vital signs- heart rate, blood pressure, temperature, weight, respiratory rate should be documented. Performance status needs to be documented on the day of study drug administration for the first 6 doses. After the first 6 doses it should be documented as deemed appropriate by the treating physician.
4. Pregnancy test should be performed within 1 week of the first dose of MK-3475 in appropriate women.
5. Patients should undergo CBC with differential count, a multiphasic profile consisting of serum electrolytes, BUN, serum creatinine, AST, ALT, serum bilirubin, alkaline phosphatase, and calcium with each treatment. . Baseline labs should be done within 2 weeks of the first dose of MK-3475. During the trial, laboratory tests can be done within 48 hours of the administration of MK-3475.
6. Patients should undergo Thyroid tests within 2 weeks of the first dose. These should be repeated at least every 4 cycles.
7. Patients should undergo appropriate scans, including brain scan, during screening, to document the status of the patient' cancer. The screening scans should be done within 3 weeks before the first dose of MK-3475. Patients should undergo appropriate scans to restage the patient after every 2 cycles for the first 6 cycles. For the first 6 cycles the re-staging scans should be performed within 1 week of the next cycle. After the first 6 cycles, the scans can be done as often as necessary by the treating physician but should be done at least every 4 cycles.
8. Archival tumor tissue will be retrieved to assess tumor PD-L1 status. Any tissue available should be submitted. Patient will be eligible even if tumor tissue cannot be submitted.
9. Patients will undergo blood collection for Circulating Tumor Cells (CTCs). This can be done on the first day of the first cycle prior to dosing MK-3475. This should also

be done on the first day of the second cycle and first day of the third cycle even if the drug is being held.

10. Patients who have completed 24 months on MK-3475 and stop therapy without progression can be retreated if patient has further progression. Patient will have to meet all original eligibility criteria and will be assessed and managed as a new patient starting on therapy. See section 8.1.6.
11. Every 12 weeks until the start of the next treatment for patient's cancer, disease progression, death, end of study.

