6.1.1 Dose Modification

6.1.1.1 Dose Modification

There is no dose reduction allowed on the protocol. However the dosing frequency can be increased from 3 weeks to every 4 weeks. MK-3475 will be withheld for drug-related Grade 4 hematologic toxicities, non-hematological toxicity \geq Grade 3 including laboratory abnormalities, and severe or life-threatening AEs as per Table 3 below. **In addition, the drug can be held for any grade of toxicity by the treating physician if it is felt that it is in the best interest of the patient**

Table 3: Dose modification guidelines for drug-related adverse events.

Toxicity	Grade	Hold Treatment (Y/N)	Timing for restarting treatment	Dose/Schedule for restarting treatment	Discontinue Subject (after consultation with Sponsor)
Hematological Toxicity	1, 2, 3*	No	N/A	N/A	N/A
	4	Yes	Toxicity resolves to Grade 0-1 or baseline	May increase the dosing interval by 1 week	Toxicity does not resolve within 12 weeks of last infusion Permanent discontinuation should be considered for any severe or life-threatening event
Non-hematological toxicity	1	No	N/A	N/A	N/A
	2	Consider withholding for persistent symptoms	Toxicity resolves to Grade 0-1 or baseline	Clinical AE resolves within 4 weeks: Same dose and schedule (reference Section 5.6.1.2 for recommendations regarding pneumonitis) Clinical AE does not resolve within 4 weeks: May increase the dosing interval by 1 week	Toxicity does not resolve within 12 weeks of last infusion

Note: Exception to be treated similar to grade 1 toxicity

- Grade 2 alopecia
- Grade 2 fatigue

For additional information regarding Adverse Events with a potential Immune-Etiology reference Section 6.3.1.1

Toxicity	Grade	Hold Treatment (Y/N)	Timing for restarting treatment	Dose/Schedule for restarting treatment	Discontinue Subject (after consultation with Sponsor)
	3, 4	Yes	Toxicity resolves to Grade 0-1 or baseline	May increase the dosing interval by 1 week	Toxicity does not resolve within 12 weeks of last infusion Permanent discontinuation should be considered for any severe or life-threatening event

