8.1.4.2 Tumor Imaging and Assessment of Disease

Patients will undergo scans to assess the status of the cancer within 3 weeks before the first dose of MK-3475. All known areas of metastases should be imaged. Patients will undergo restaging scans every 2 cycles for the first 6 cycles. Subsequently they can be done as often as necessary, but should be done at least every 4 cycles.

The treating physician will decide which scans need to be done to appropriately assess the status of the cancer.

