8.1.6.1 Follow-up Visits

Subjects who discontinue trial treatment for a reason other than disease progression will move into the Follow-Up Phase and should be assessed every 12 weeks by radiologic imaging to monitor disease status. Every effort should be made to collect information regarding disease status until the start of new anti-neoplastic therapy, disease progression, death, end of the study or if the subject begins retreatment with MK-3475 as detailed in Section 8.1.6.1.2

Subjects who are eligible to receive retreatment with MK-3475 according to the criteria in Section 8.1.6.1.2 will move from the follow-up phase to the Second Course Phase when they experience disease progression.

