10.2 Secondary Endpoints-

Modified Progression Free Survival- Modified PFS requires that RECIST defined PFS is confirmed by a second scan at least 4 weeks apart. Following issues need to be considered

- a. New lesion/lesions are considered as progression in RECIST defined PFS. However for modified PFS the largest unidirectional measurement of new lesion/lesions will be added to the total tumor measurement. If this exceeds 20% on 2 consecutive scans then the patient will be considered to have tumor

progression according to modified PFS criteria. A new lesion or lesions alone will not qualify for this modified PFS definition.

- b. If patients who have RECIST defined progression are symptomatic or have decline in performance status or develop unacceptable laboratory abnormalities and the treating physician and/or the patient decide to discontinue therapy or change therapy then the second scan confirming progression is not required.

Overall Survival- Overall survival is defined as the time from registration to time of death. If the patient is lost to follow-up, survival will be censored on the last date the patient was known to be alive.

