11.3 Analysis plan for primary and secondary endpoints

The primary endpoint, PFS, will be estimated with the standard Kaplan-Meier method, from which summary statistics of interest (median, 1-year rate, etc.) will be derived. Both point and 95% confidence interval estimates of PFS will be calculated. In this trial we will also assess PFS using modified criteria as well. It is well recognized that patients treated with immune therapy may have pseudo progression or can have delayed response. The modified PFS requires RECIST defined progression on 2 sequential scans at least 4 weeks apart for definition of progression. Overall survival is defined as the time from start of treatment to time of death. If the patient is lost to follow-up, survival will be censored on the last date the patient was known to be alive. All time-to-event endpoints will be estimated using standard Kaplan-Meier methods, from which the median and confidence interval will be calculated. Point and exact confidence interval estimates will be calculated for the toxicities and response rates. Cox model will be used to evaluate the association between time to event outcomes and covariates such as PD-L1 status and CTCs.

PD-L1 (yes/no) in tumor tissue and circulating tumor cells (CTCs) will be measured and their association will be studied with logistic regression. We will explore associations between PD-L1 and PFS, modified PFS, and OS using the Cox model. If biopsy samples are 15 patients or less, statistical analysis will be descriptive.

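### Required scans widen from every 6 to every 12 weeks after cycle 6, so the planned Kaplan-Meier 1-year PFS rate can be as high as the week-42 rate

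*Combined protocol and SAP*

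**What the plan says.** The Combined protocol and SAP sets the minimum scan schedule in two places that agree.

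- Section 7.1, footnote 7: sites are to "restage the patient after every 2 cycles for the first 6 cycles", after which "the scans can be done as often as necessary by the treating physician but should be done at least every 4 cycles".
- Section 8.1.4.2: "Subsequently they can be done as often as necessary, but should be done at least every 4 cycles".

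Cycle length comes from section 7.1, footnote 3: "MK-3475 will be administered at a dose of 200 mg IV every 3 weeks for a maximum of 2 years". Section 6.1.1.1 lets it stretch: "However the dosing frequency can be increased from 3 weeks to every 4 weeks". Under section 8.1.6.1, patients who stop the drug without progression "should be assessed every 12 weeks by radiologic imaging to monitor disease status".

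Section 10.1 counts PFS from registration and dates a death without prior progression on the day of death. Section 11.3 estimates PFS by Kaplan-Meier, from which "summary statistics of interest (median, 1-year rate, etc.) will be derived". It does not mention that progression is known only to lie between two scans.

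**The concern.** One year (week 52) lies inside a 12-week stretch with no required scan. A patient who progresses without symptoms at week 45 and is scanned only as required is recorded as progressing at week 54, and so counts as progression-free at 1 year. The error runs in one direction, towards a higher rate. With a single arm, there is no control group on the same schedule in which the same error would appear.

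At stake is the only fixed-time rate that section 11.3 names for the primary endpoint. A reader will take it as PFS at 12 months, when part of it may be PFS at about 10 months.

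**Working it through.** **The plan's own figure.** Section 11.2 gives exponential PFS, median 2 against 3 months, one-sided alpha 0.05, 80% power, 18 months of accrual and at least 6 months of follow-up.

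- Events needed: ((1.645 + 0.842)/ln 1.5)² = 37.6.
- Probability of an event at median 3 (λ = ln 2/3): 1 − (e^(−6λ) − e^(−24λ))/(18λ) = 0.941.
- N = 37.6/0.941 = 39.97, so 40. Then 40/0.90 = 44.4, so 45 enrolled. Both match the plan.

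**Scan calendar on 3-week cycles.** Scans after cycles 2, 4, 6, 10, 14 and 18 fall at weeks 6, 12, 18, 30, 42 and 54. The last required scan before week 52 is at week 42.

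**Bound on the 1-year rate.** With 52/12 weeks per month, a 3-month median is 13 weeks and a 2-month median is 8.67 weeks, so S(w) = 2^(−w/13) or 2^(−w/8.67). The plan gives no rule for dating progression; I assume the date of the scan that shows it. If every event is found at a required scan, the curve at week 52 equals S(42). Had scans stayed 6-weekly, it would equal S(48).

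| | Median 3 months | Median 2 months |
|---|---|---|
| True rate, S(52) | 6.25% | 1.56% |
| 12-weekly scans, S(42) | 10.65% | 3.48% |
| 6-weekly scans, S(48) | 7.74% | 2.15% |
| Total ratio, S(42)/S(52) | 1.70 | 2.23 |
| Ordinary scan dating, S(48)/S(52) | 1.24 | 1.38 |
| Widening alone, S(42)/S(48) | 1.38 | 1.62 |
| Shift, S(42) − S(52) | 4.4 points | 1.9 points |

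Among 40 patients the bound is 4.3 against 2.5 (median 3) or 1.4 against 0.6 (median 2).

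**Events dated on time.** Deaths, and progressions caught by an earlier scan, are dated close to when they occur. For a share q of such events, the reported rate is S(52) + (1 − q)[S(42) − S(52)]. The documents do not give q, so this is a range of assumptions.

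| q | Median 3 months | Median 2 months |
|---|---|---|
| 0 | 10.65% (1.70) | 3.48% (2.23) |
| 0.25 | 9.55% (1.53) | 3.00% (1.92) |
| 0.50 | 8.45% (1.35) | 2.52% (1.61) |
| 0.75 | 7.35% (1.18) | 2.04% (1.31) |

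**Sensitivity.**

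- A 365.25-day year gives ratios of 1.72 and 2.25.
- Counting from registration, with the first dose 5 days later, puts the scan at week 42.71 and gives 1.64 and 2.10.
- If PFS is longer than planned, the ratio falls: 1.49 at a 4-month median and 1.31 at 6 months.
- Stretched cycles move the last scan either way. With 4-week cycles after cycle 6 the scans are at weeks 34, 50 and 66, and at median 3 the ratio is 2^(2/13) = 1.11. With 4-week cycles after cycle 2 they are at weeks 6, 14, 22, 38 and 54, and the ratio is 2^(14/13) = 2.11.

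**Reach.** The design medians, at 8.7 and 13.0 weeks, lie inside the 6-weekly period. At week 18, S is 23.7% (median 2) or 38.3% (median 3), so the Kaplan-Meier median is reached before the interval widens.

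**The case against.** The strongest reply is that week 42 is an extreme case. It needs every patient on 3-week cycles, no scan beyond the minimum, and every event to be a scan finding. Deaths are dated exactly, and the protocol expressly allows extra scans. All of this stands, so the reported rate lies between the week-52 and week-42 rates. The protection is partial, though. Footnotes 1 and 3 of section 7.1 also let clinical review thin after cycle 6, with examinations every other cycle and performance status recorded at the physician's discretion.

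The second reply is that little depends on it. The 1-year rate is an example in a parenthesis. The design tests the median, and sections 4.1 and 4.2.3 give a historical median but no historical 1-year rate. The exact 95% interval for 4 of 40 is 2.8% to 23.7%, far wider than the shift. The ratios are large because the true rates are close to zero. This also stands, and it makes the point a modest one. It does not remove the bias, because a wide interval centred too high is still centred too high.

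A reader might also infer that late confirmation of progression takes twice as long, so that the gap between RECIST PFS and modified PFS grows through scan spacing alone. The documents do not support that. Section 10.2 says "Modified PFS requires that RECIST defined PFS is confirmed by a second scan at least 4 weeks apart", which sets a minimum and does not tie confirmation to the next required scan. It does not say whether the first or the confirming scan dates the event; if the first does, the wait adds no time to modified PFS. It also waives the second scan for patients who are symptomatic or declining and whose therapy is stopped or changed.

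**Conclusion.** The point holds as a bound. On 3-week cycles the 1-year Kaplan-Meier PFS rate can be as high as the week-42 rate: 10.7% against 6.25% at a 3-month median, or 3.5% against 1.6% at a 2-month median. With half of events dated on time it would be 8.5% or 2.5%. These figures assume exponential PFS to 1 year and progression dated at the scan; a hazard that falls late would shrink them.

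Two stronger readings should be resisted. The 1-year rate is not simply a week-42 rate under another name, because deaths and extra scans are dated when they occur. Nor is the whole 1.7 to 2.2-fold ratio due to the wider interval: that accounts for about 1.4 to 1.6, and ordinary scan dating for the remaining 1.24 to 1.38. The widening leaves the primary median and the sample size of 40 as they are. The change is worth making because it is cheap and the bias has a known direction.

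**What to change.** Change section 11.3 only, in one of two ways.

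- Replace the 1-year rate with PFS rates at scheduled scan times, labelled as such, for example weeks 18, 42 and 54. State when after each scheduled scan the curve is read, so that a scan a few days late is counted. Patients on stretched cycles or in off-drug follow-up will not match these weeks exactly.
- Keep the 1-year rate and add an interval-censored sensitivity estimate, using the last progression-free scan and the first scan showing progression, with deaths at their exact dates. A nonparametric version may only bound the rate between the week-42 and week-54 values. With S(54) = 2^(−54/13) = 5.6%, that is 5.6% to 10.7% at median 3; with 2^(−54/8.67) = 1.3%, it is 1.3% to 3.5% at median 2. State the bounds, or name the parametric model used.

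The cost is SAP wording, one extra analysis from scan dates the trial needs anyway, and a less favourable 1-year figure. No change to the scan schedule is needed.

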2.0 TRIAL DESIGN

2.1 Trial Diagram

The primary end point of the study is to assess Progression Free Survival (PFS) by RECIST 1.1. However it is well recognized that patients on immune check point inhibitors may experience pseudo-progression or can have delayed response. Therefore patients who do not have development of significant signs or symptoms of progression or significant decline in performance status or the patient/the treating physician feel the need to start next treatment, will require evidence of progression on 2 scans more than 4 weeks apart. Both RECIST defined PFS and **this modified PFS** will be reported for all patients enrolled on the trial.

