8.1.6.1.1 Survival Follow-up

Once a subject experiences confirmed disease progression according to modified response criteria or starts a new anti-cancer therapy, the subject moves into the survival follow-up phase and should be contacted by telephone every 12 weeks to assess for survival status until death, withdrawal of consent, or the end of the study, whichever occurs first.

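### A symptom-free patient who changes treatment after a first RECIST progression may never have the second scan that 10.2 requires, so modified PFS can exceed RECIST PFS without any pseudo-progression

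*Combined protocol and SAP*

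**What the plan says.** **The endpoint.** Secondary objective 1 (3.2) points to 10.2 for the definition: "Modified PFS requires that RECIST defined PFS is confirmed by a second scan at least 4 weeks apart".

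**When the second scan is not needed.** Three sections differ.
- 10.2(b) waives it when a RECIST progressor has symptoms, performance decline or unacceptable laboratory values and the physician or patient decides to stop or change therapy. However the conjunctions are grouped, a patient with none of the three conditions is outside the waiver.
- 2.1 opens its list with a negative (patients without signs of progression or decline) and continues "or the patient/the treating physician feel the need to start next treatment, will require evidence of progression on 2 scans". On the natural reading, the need for next treatment is by itself a reason not to require two scans.
- 11.3 repeats the two-scan requirement and gives no waiver.

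**When disease imaging ends for patients off drug.** Four places differ.
- Footnote 11 in 7.1: "Every 12 weeks until the start of the next treatment for patient's cancer, disease progression, death, end of study".
- 8.1.6.1: "Every effort should be made to collect information regarding disease status until the start of new anti-neoplastic therapy, disease progression, death".
- 6.5: "After documented disease progression each subject will be followed by telephone for overall survival".
- 8.1.6.1.1 starts survival follow-up later: "Once a subject experiences confirmed disease progression according to modified response criteria or starts a new anti-cancer therapy".

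Footnote 11, 8.1.6.1 and 8.1.6.1.1 all end disease follow-up when new cancer therapy starts.

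**Analysis rules.** The death and censoring rules in 10.1 and 11.1 are written for RECIST PFS. Neither 10.2 nor 11.3 says how an unconfirmed progression is analysed, whether death is a modified-PFS event, or whether a confirmed progression is dated at the first or the second scan.

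**The concern.** Modified PFS was added because a first progression on a checkpoint inhibitor may be pseudo-progression or precede a delayed response. Both versions are to be reported for all enrolled patients (2.1), so a reader will take the gap between them as a sign of that phenomenon.

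The gap can also arise from missing scans. A symptom-free patient with a genuine progression who moves to another treatment fails the 10.2(b) waiver and has no further protocol imaging. A symptom-free patient who progresses after stopping drug for another reason may also have no second scan, depending on which follow-up passage the site applies. In either case the RECIST event has no counterpart in modified PFS at that date. Censoring patients at the moment they progress is informative, and waiting for their death puts the event too late. Both push modified PFS upward.

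**Working it through.** **1. The plan's own figure.** 11.2 gives 40 patients for 80% power, one-sided alpha 0.05, exponential PFS, median 2 against 3 months, 18 months' accrual and 6 months' minimum follow-up.
- Events: (1.645 + 0.842)² / (ln 1.5)² = 37.6.
- P(event), with λ = ln 2 / 3: 1 − (e^(−6λ) − e^(−24λ)) / (18λ) = 0.941.
- N = 37.6 / 0.941 = 39.97, so 40. Allowing for 10% ineligible, 40 / 0.9 = 44.4, so 45.

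The figure reproduces. It concerns RECIST PFS only; no figure is stated for modified PFS.

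**2. Who can lack a second scan.**
- *Still on drug, no switch.* Not affected: the progression ground for leaving the trial in 6.5 is "Confirmed radiographic disease progression according to modified response criteria", so scanning continues.
- *Declining and stopping or changing therapy.* Covered by 10.2(b).
- *Symptom-free and switching.* Outside 10.2(b), inside 2.1, not addressed in 11.3; imaging ends with the new therapy.
- *Already off drug, symptom-free, no new therapy.* Footnote 11, 8.1.6.1 and 6.5 point to stopping at the first progression; 8.1.6.1.1 points to continuing.

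**3. Size under censoring (illustration).** Inputs from the documents: a 2-month median (11.2) and scans every two 3-week cycles (Table 2, 8.1.4.2), so weeks 6, 12 and 18. Assumptions: exponential PFS, no pseudo-progression, confirmed progression dated at the first progression scan, and a random share u of progressors with no second scan, censored at the progression scan.
- Six weeks = 42 / 30.44 = 1.38 months. Probability of progression per interval = 1 − 2^(−1.38/2) = 0.380.
- Kaplan-Meier at scan k: (1 − 0.380(1 − u))^k.

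| Share u | Week 12 | Week 18 |
|---|---|---|
| 0 | 0.384 | 0.238 |
| 5% | 0.408 | 0.261 |
| 10% | 0.433 | 0.285 |
| 20% | 0.484 | 0.337 |
| 30% | 0.539 | 0.395 |
| 40% | 0.596 | 0.460 |

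The Kaplan-Meier median stays at the week-12 scan (2.8 months) until 1 − 0.380(1 − u) exceeds √0.5 = 0.707, that is u above about 23%. It then jumps to the week-18 scan (4.1 months). The size of that jump reflects the scan grid.

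**4. Dependence on the rule.** With a true 3-month median and progression times taken as exact, censoring at progression gives a median of 3/(1 − q) for an affected share q. Counting these patients at death was simulated with an assumed median survival after progression of 3 to 8 months.

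| Share q | Censored at progression | Counted at death | Counted at RECIST date |
|---|---|---|---|
| 10% | 3.33 | 3.3–3.4 | 3.0 |
| 20% | 3.75 | 3.7–3.9 | 3.0 |
| 30% | 4.29 | 4.1–4.6 | 3.0 |
| 40% | 5.00 | 4.5–5.5 | 3.0 |

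The first two rules inflate the median by similar amounts. The third leaves no artificial gap at any share.

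**The case against.** **The intent is visible elsewhere.** 2.1 exempts patients who need next treatment, and the efficacy-endpoint rationale in section 4 lets a patient leave therapy for any reason before the modified criteria are met. An analyst could apply 2.1 and avoid the problem. This stands in part, but the rationale sentence governs therapy and not the endpoint, and objective 1 names 10.2 as the definition. Following 10.2 as written drops these events.

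**Off-drug imaging.** A reader might infer that imaging of off-drug patients simply ends at the first progression. The documents do not settle that. 8.1.6.1.1 holds patients out of survival follow-up until confirmed progression or new therapy, and the shorter wording elsewhere can be read in that light. This is a conflict between passages.

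**The share may be small.** 4.2.1 says adverse events infrequently require discontinuation, and symptomatic progressors who stop or change therapy are already covered by 10.2(b). At 5% the week-18 estimate moves about 2 points. At 10% it moves 28.5 − 23.8 = 4.7 points, less than one standard error with 45 patients (√(0.238 × 0.762 / 45) = 6.4 points). Off-drug patients are also scanned every 12 weeks, so the 6-week grid suits on-drug switchers only. All of this stands. Sampling error does not remove a bias that runs one way, but it limits what the larger shares can be used to claim.

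**Low consequence.** Modified PFS is secondary and estimated by Kaplan-Meier, with exploratory Cox associations and no test against a historical value. RECIST PFS is reported beside it. This stands and bears on priority.

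**Conclusion.** The point holds for this secondary endpoint. 10.2(b) is narrower than 2.1, 11.3 has no waiver, and imaging ends at new therapy. A real progression in a symptom-free patient who switches therefore need not produce a modified-PFS event at that date. For patients already off drug, 6.5, footnote 11 and 8.1.6.1 conflict with 8.1.6.1.1.

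Modified PFS can exceed RECIST PFS with no pseudo-progression. A reader might infer that it will, but that needs at least one such patient and a rule that censors the progression or waits for death. The plan states no rule, and counting at the RECIST date removes the effect.

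The illustrated size is about 2 to 16 percentage points at week 18 for shares of 5% to 30%. It rests on an assumed share, an exponential 2-month median and censoring at the progression scan. The primary endpoint, the 45 patients and the power are unaffected. The text should be corrected before analysis, since handling chosen afterwards in so small a trial would be discretionary.

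**What to change.** 1. In 10.2(b) and 11.3, state that a RECIST progression with no later disease scan, or followed by a change of cancer treatment for any reason before a second scan, is a modified-PFS event on the date of that RECIST progression. This brings both sections into line with 2.1.
2. In the same edit, state that death without prior progression is a modified-PFS event, and that confirmed progression is dated at the first progression scan. Dating at the second scan would add at least 4 weeks to every confirmed event, again without pseudo-progression.
3. Reconcile 6.5, footnote 11, 8.1.6.1 and 8.1.6.1.1 on when disease imaging ends.
4. Report how many progressions had no second scan, with a sensitivity analysis that censors them.

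The cost is wording and one extra analysis. Sample size and the primary analysis do not change. The downside is a slightly less favourable modified PFS, because a pseudo-progression in a patient who switched early would be counted as an event.
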